## **The impact of hydroxybutyl chitosan and 5-Fluorouracil on the procedure of endoscopic endonasal dacryocystorhinostomy.**

### **1. Background**

Endoscopic endonasal dacryocystorhinostomy (Endo-DCR) has the advantages of less surgical trauma, shorter time, less postoperative bleeding, faster recovery, and no skin scarring. However, the success rate of Endo-DCR surgery still varies widely between 58% and 94%, and the reason for surgical failure is mainly due to the membranous closure of the lacrimal sac-nasal anastomosis. The application of new filling materials to the lacrimal sac-nasal anastomosis provides a new way to improve the success rate of Endo-DCR.

Chitosan (CS) is a natural cationic polysaccharide, chemically named poly-2-amino-2-deoxy B-D-glucose, which has good biocompatibility and biodegradability, and is a new type of natural medical biomaterials. CS also has the advantages of abundant sources, no need for refrigeration, can be sterilized by autoclaving, and low price. Several studies have demonstrated the safety and efficacy of CS products for Endo-DCR. CS as hemostatic dressing for Endo-DCR is superior to collagen hemostatic agents. The success rate of CS-assisted Endo-DCR is higher than that of unassisted control group. However, chitosan is not easily soluble in water, making its application somewhat limited.

Hydroxybutyl chitosan (HBCS), a CS ether synthesized by substituting hydroxybutyl for the hydroxyl and amino groups of CS, maintains the nontoxic, biocompatible, biodegradable, antimicrobial, and moisturizing properties of CS, and the hydroxybutylation confers water-solubility and temperature-sensitivity to CS. Therefore, it is also widely used in biomedical applications such as postoperative adhesion prevention, tissue engineering, drug delivery and wound healing, etc. Materials made of HBCS, complexes of HBCS, and derivatives of HBCS have been shown to be safe and effective wound dressings with antimicrobial and blood coagulation promoting effects. Used for this trial proposed to be used is a heterophasic system of synthesized hydroxybutyl chitosan, this HBCS undergoes a sol-gel transition at a critical temperature (37 degrees Celsius), which facilitates clinical manipulation while accurately localizing around the anastomosis, preventing postoperative adhesions, and inhibiting the growth of fibroblasts. The role of HBCS in wound healing has been shown to have definitive therapeutic efficacy in clinical applications, and in ophthalmology also has some applications.

5-Fluorouracil (5-FU) is an antimetabolic drug that inhibits protein synthesis by suppressing the biochemical activities of rRNA and mRNA in the nucleus; it also induces the growth of apoptotic genes. In recent years, 5-FU has been found to be effective in the treatment of keloid

scars. It has now been widely used both at home and abroad to inhibit fibroblast proliferation and scar formation in the filtration vesicles after glaucoma filtration surgery, with good safety and efficacy. In antimetabolites as DCR adjuvant therapy significantly increased the size of the opening and improved the success rate of surgery.

## **2. Aims:**

To investigate the effects of HBCS with and without 5-FU during Endo-DCR.

## **3. Induction and Exclusion Criteria**

### **3.1 Induction Criteria:**

- 1) Age: 18 years or above;
- 2) Gender: unlimited;
- 3) Disease duration: unlimited;
- 4) Indications: patients diagnosed with chronic dacryocystitis;
- 5) Subjects have a strong need for treatment, fully understand the condition and sign an informed consent form.

### **3.2 Exclusion Criteria:**

- 1) Those who do not meet the inclusion criteria;
- 2) Those who are allergic to hydroxybutyl chitosan and 5-fluorouracil;
- 3) Those who have suffered from blepharitis, blepharitis, entropion, ectropion, keratitis, lacrimal tumors and other diseases of the external eye, ocular surface and other lacrimal apparatus within three months, or

those who have undergone ocular surgery;

- 4) Those who suffer from chronic dacryocystitis and have a history of lacrimal duct placement;
- 5) Those who suffered from lacrimal surgery or lacrimal fistula;
- 6) Those who have used glucocorticoid sprays such as Cochlearia within three months.
- 7) Those with a history of facial trauma (eyelid trauma, nasal trauma, etc.) or facial surgery within three months;
- 8) Those with nasal abnormalities or nasal diseases (nasal polyps, nasal tumors, sinusitis, turbinate hypertrophy, nasal bone fracture, etc.) within three months or those who have undergone nasal surgery;
- 9) Facial paralysis or severe eyelid laxity or other causes of tearing;
- 10) Those who also suffer from autoimmune diseases, bleeding disorders, renal insufficiency dialysis treatment and other serious systemic diseases, or those who have a debilitating general condition;
- 11) Those with blisters or shingles;
- 12) Those who also have more serious skin diseases such as acne, rosacea or previous history of physical scarring;
- 13) Medical, personal and allergic history that, in the judgment of the investigator, may interfere with the results of the test or increase the risk to the patient;
- 14) Participation in a clinical trial of another drug within the last 3

months;

15) Those who are unable to follow up on the scheduled visits or who are unable to cooperate with the investigator.

#### **4. Exit Criteria**

1) Patients who could not or did not undergo the procedure for various reasons, such as the occurrence of certain comorbidities, complications, or specific physiological changes in the subject that make continuation of the procedure inadvisable;

2) Patients whose surgical procedure was changed for various reasons.

3) Withdrawal of informed consent before the end of the study,

including:

a. Withdrawal from the study due to unsatisfactory efficacy or without any reason;

b. The occurrence of an adverse event or serious adverse event that, in the opinion of the physician, warrants termination of further clinical trials;

c. Poor compliance and inability to complete the review, resulting in incomplete information and affecting the determination of efficacy.

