## 8. Flow-up

		1 day	1 week (±1 day)	2 weeks (±1 day)	4 weeks (±3 days)	8 weeks (±3 days)	12 weeks (±7 days)	>24 weeks
Subjective perception	Comfort	√						
	Bleeding	√						
	Epiphora, mucopurulent discharge	√	√	√	√	√	√	√
Specimen collection	conjunctival sac		√	√	√	√		
	nasal cavity				√			
Endoscope						√	√	√

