## 9. Expected Risks and Measures to Address Them

1) En-DCR is an invasive procedure and there is a risk of blood leakage from the lacrimal sac-nasal anastomosis in the early postoperative period.

Most of the distant cases fail due to mucosal epithelial tissue hyperplasia, scarring and obstruction of the anastomosis. HBCS can stop diffuse bleeding, inhibit bacteria, and promote wound healing, etc. 5-FU can effectively inhibit the proliferation of fibroblasts. However, the effect of the two as dressings at the anastomosis of the lacrimal sac and nasal mucosa applied to En-DCR is uncertain. We will take appropriate measures if the following situations occur.

- a. Localized infection: intensive anti-infection treatment.
- b. Severe postoperative bleeding: Use other drugs and dressings to stop bleeding.
- c. Granulation tissue, scar proliferation and anastomotic adhesion: excise or separate them, and apply antiproliferative drugs to the wound.
- d. Delayed healing: use other dressings and medications.

2) Adequate and repeated education, obtaining informed consent, establishing timely and effective communication with patients, and standardized follow-up.

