## **10. Statistical methods**

To compare the differences between the adjuvant therapeutic effects of different En-DCR in the three groups: data were analyzed using SPSS 19.0 software, one-way ANOVA was used for age comparison, and Kruskal-Wallis H-test was used for comparison of postoperative comfort and blood leakage. Comparison of gender, complications, and cure rate

was performed by chi-square test, and the difference was considered statistically significant at  $P<0.05$ . Effective rate was compared by Fisher's exact probability method, and  $P<0.05$  was regarded as statistically significant difference, and  $P<0.0167$  was regarded as statistically significant difference for two-by-two comparison. The collected conjunctival sac and nasal flora were analyzed: alpha diversity analysis, PCA analysis, taxonomic composition analysis, and Lefse analysis were used, and differences were considered statistically significant at  $P<0.05$ . Comparisons between groups were made using chi-square test or fisher's exact probability method for adverse events and serious adverse events when necessary.

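### Unsatisfactory efficacy is a listed exit before 6 months, but the plan has no analysis set or exit rule, so the cure and effective rates may omit failures

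*Combined protocol and SAP*

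**What the plan says.** Section 4 (Exit Criteria) lists who leaves the study. Criterion 1 covers patients who did not undergo the procedure. Criterion 2 is "Patients whose surgical procedure was changed for various reasons". Criterion 3, withdrawal of consent before the end of the study, has three items:

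- "a. Withdrawal from the study due to unsatisfactory efficacy or without any reason"
- "The occurrence of an adverse event or serious adverse event that, in the opinion of the physician, warrants termination" (the item goes on to name further trial participation)
- "Poor compliance and inability to complete the review, resulting in incomplete information and affecting the determination of efficacy"

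Section 7 puts the endpoint at 6 months after surgery. Section 5 plans 40 patients in each of three groups. Section 10 assigns the chi-square test to "Comparison of gender, complications, and cure rate" and Fisher's exact test to the effective rate, with thresholds of 0.05 overall and 0.0167 for pairwise comparisons.

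No section defines an analysis set, a denominator, a rule for missing outcomes or a sensitivity analysis. The terms cured and effective are not defined either.

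The section 8 schedule records "Epiphora, mucopurulent discharge" at every visit from day 1, and endoscopy at 8, 12 and more than 24 weeks. A patient who leaves early may therefore have usable outcome data on file, but nothing says whether those data feed the 6-month rates.

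**The concern.** One named exit reason is treatment failure in substance, and another is an outcome that could not be determined. The remaining reasons (an adverse event, a changed operation) are tied less directly to outcome. A changed operation, or an operation not done, is a post-randomisation exit only if allocation comes before surgery, which section 6 does not state.

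Faced with a patient who left dissatisfied at 10 weeks, an analyst could count a failure, carry forward the last recorded status, or omit the patient. All three fit the text, they give different rates, and the choice could be made after the results are known. Omission raises the reported success of every arm that loses failures. If the arms lose them at different rates, the comparison is biased in a direction that cannot be known in advance.

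**Working it through.** **Inputs.** From the documents: 40 per arm, three arms (section 5); thresholds 0.05 and 0.0167 (section 10); published success of 58% to 94% (section 1), used only to choose plausible counts. Assumed: all cure counts and exit rates, because the documents give none.

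**Plan's own figures.** 3 × 40 = 120 and 0.05/3 = 0.0167 both reproduce. The sample size itself cannot be reproduced, since no power, target rates or dropout allowance are given. The 0.0167 stands in the sentence on Fisher's test; I apply it to pairwise comparisons of either rate.

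**Step 1: failures per arm.** 40 × (1 − 0.94) = 2.4 and 40 × (1 − 0.58) = 16.8, so about 2 to 17.

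**Step 2: inflation of one arm's rate.** With s successes, f failures and a fraction q of failures exiting uncounted, the reported rate is s / (s + f(1 − q)). For 32/40 = 80%:

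- q = 25%: 32/(32 + 6) = 84%
- q = 50%: 32/(32 + 4) = 89%

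**Step 3: a real difference lost.** Control 29/40 v test 38/40, two-sided Fisher:

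| Control failures dropped | Control | P |
|---|---|---|
| 0 | 29/40 | 0.013 |
| 2 | 29/38 | 0.023 |
| 4 | 29/36 | 0.076 |

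Uncorrected chi-square agrees. With none dropped, 80 × (29×2 − 11×38)² / (40×40×67×13) = 7.44, P = 0.006. With two dropped, 78 × (29×2 − 9×38)² / (38×40×67×11) = 5.62, P = 0.018. Two dropped failures move either test above 0.0167.

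**Step 4: a difference created.** First arm 28/40, second arm starting at 34/40:

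| Failures dropped, second arm only | Second arm | Fisher P | Chi-square P |
|---|---|---|---|
| 0 | 34/40 | 0.180 | 0.108 |
| 2 | 34/38 | 0.049 | 0.033 |
| 3 | 34/37 | 0.021 | 0.015 |
| 4 | 34/36 | 0.007 | 0.006 |

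Crossing 0.0167 takes four of the six failures by Fisher, or three by chi-square, with none leaving the other arm. If two leave the second arm and one leaves the first, 28/39 v 34/38 gives Fisher P = 0.083.

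**Step 5: three-group false-positive rate.** Simulation with equal true cure in all arms and 40 per arm. Each failure exits with the stated probability, and a chi-square test at 0.05 is applied to those who remain.

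| Failures exiting, by arm | Cure 70% | Cure 80% | Cure 90% |
|---|---|---|---|
| 10/10/25% | 6.1% | 5.7% | 4.9% |
| 25/25/50% | 9.4% | 7.8% | 5.3–5.5% |
| 50–75%, one arm only | 21–53% | 16–38% | 9–16% |

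With no exits the rate at 80% cure is 4.9%. Equal exits do not raise it (5.0% at 80% cure with 25% of failures exiting everywhere), but they cost power: with cure 65/80/90%, power falls from 0.69 to 0.58 when 25% of failures leave each arm.

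**Step 6: effect of a rule.** Counting efficacy exits as not cured restores 28/40 v 34/40 (P = 0.180) and the 4.9% rate. The same rule should not be spread over every exit. If 10% of one arm leaves for adverse events unrelated to patency, scoring them all as failures gives a false-positive rate of 13.0%, against 5.0% if they are left out.

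**The case against.** A reader might infer that the plan excludes treatment failures from its rates. It does not say so. Section 4 says who leaves the study, section 10 is silent on them, and harm needs two further steps: failures must leave, and they must then go uncounted.

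There are grounds for expecting few efficacy exits. The study materials are applied once, at surgery, so there is no continuing treatment to abandon. Section 9 provides further care for a failing anastomosis ("Granulation tissue, scar proliferation and anastomotic adhesion: excise or separate them") and does not call those patients exits. Exclusion 15 screens out "Those who are unable to follow up on the scheduled visits or who are unable to cooperate with the investigator", which should reduce incomplete review, though it does not address withdrawal for poor efficacy. These are inferences about frequency and do not supply the missing rule.

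A reader might also infer that two or three lost failures would readily create a significant pairwise result, or that false-positive rates of 16–38% are to be expected. Neither is supported. Step 4 needs three or four one-sided exits, and the 16–38% range belongs to 80% cure with half or more of one arm's failures leaving and none elsewhere. Under moderate exits the inflation is small, and at 90% cure it is slight.

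Two objections bear on the remedy, and both stand. A patient who leaves dissatisfied early is not certain to be a 6-month failure, so an automatic failure rule can err the other way and needs a sensitivity analysis. And exits cannot be classified from interim records until cured and effective are defined.

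**Conclusion.** The point holds as an omission with a specific consequence, and should be fixed. Because one listed exit reason is itself failure, leaving the denominator open is more than a missing formality: rates computed on patients with a 6-month result would tend to overstate success, and unequal exits would bias the comparison. It should not be read as a stated rule to drop failures.

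The likely size is a few percentage points on a reported cure rate, a false-positive rate of about 6–9% instead of 5% under moderate unequal exits at 70–80% cure, and some loss of power if exits are equal. The most fragile case is a real difference near the 0.0167 threshold, where two uncounted control failures can remove significance. All of this rests on assumed counts and exit rates. Confidence is medium, because the number of exits and how they would be handled are unknown.

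**What to change.** Add to sections 4 and 10:

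1. Analyse all randomised, operated patients in their assigned group, including those whose operation was changed. Report by arm those randomised but not operated on (exit criterion 1).
2. In the primary analysis, count exits for unsatisfactory efficacy as not cured and not effective. As a sensitivity analysis, classify them instead from their last recorded symptoms and endoscopy.
3. Classify other exits without a 6-month result from the symptom and endoscopy records already scheduled in section 8, as far as consent allows, using the same definitions of cured and effective as at 6 months. Those definitions must be written down. Add completer and best-case/worst-case sensitivity analyses.
4. Record unsatisfactory efficacy separately from withdrawal without a reason, which item a of criterion 3 now merges. Report exits by arm and reason, and keep all treated patients in the complication and adverse-event denominators.

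Cost: a short addition to two sections, the outcome definitions, and one more recorded field. No patients or visits are added. Stated cure rates will be slightly lower and there is a little more analysis. Patients who leave before the first endoscopy at 8 weeks can be classified from symptoms only, so some results will stay uncertain and rest on the sensitivity analyses.

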## 6. Treatment

With random table, the patients were randomly divided into three groups. In group A, HBCS was applied to the surface of the anastomosis of the nasal mucosal flap and the lacrimal sac mucosal flap. During the aforesaid procedure, 0.3 ml of 5-FU solution (25 mg/ml) was injected under the nasal mucosa around the anastomosis in group B. (Sup.1)

Anastomoses in Group C patients were covered with gelatin sponges encapsulated with thrombin, tobramycin dexamethasone, and oculentum.

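### Exit criterion 3b lets a physician-judged adverse event end participation after a one-time surgical exposure, so what it ends is the follow-up of the patients with the most concerning events

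*Combined protocol and SAP*

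**What the plan says.** **Exit rule.** Section 4 has three exit criteria. The third is headed "Withdrawal of informed consent before the end of the study", and its item b is "The occurrence of an adverse event or serious adverse event that, in the opinion of the physician, warrants termination of further clinical trials". The trigger is therefore conditional on the physician's judgement, yet the item sits under a heading about the patient's own consent.

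**Exposure.** Section 6 places all study material in the operation:
- Group A: "HBCS was applied to the surface of the anastomosis of the nasal mucosal flap and the lacrimal sac mucosal flap".
- Group B (HBCS with 5-FU, per section 5): "During the aforesaid procedure, 0.3 ml of 5-FU solution (25 mg/ml) was injected under the nasal mucosa around the anastomosis in group B".
- Control: "Anastomoses in Group C patients were covered with gelatin sponges encapsulated with thrombin".

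No later application or injection as study treatment appears anywhere. The supplement cited in section 6 (Sup.1) is not part of the text available for this review.

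**Follow-up.** Section 7 sets the endpoint at 6 months. Section 8 schedules seven visits, with endoscopy at the last three.

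**Safety.** Section 9 lists four kinds of postoperative problem with a response to each, for example "Delayed healing: use other dressings and medications", and asks for standardized follow-up in general terms. Section 10 compares complications between groups and plans chi-square or Fisher tests "for adverse events and serious adverse events when necessary". No section says what happens to observation after a 3b exit, or which patients form the denominator of these comparisons.

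**The concern.** Where treatment is ongoing, taking a patient off it because of an adverse event limits further exposure. Here, by the time a postoperative event occurs, the study material is already in place. What remains of the trial is symptom questions, specimens and endoscopy, so an exit mainly ends observation.

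The patients affected are those whose events a physician thought serious enough to act on, so the loss is not random. If one arm produces more such events, it also loses more follow-up. Section 9 itself says the effect of the two materials at the anastomosis is uncertain, and attributes most distant failures to tissue overgrowth, scarring and obstruction. The scheduled endoscopies are the trial's direct view of those. At stake are the duration and outcome of the worst events and the later complications in the same patients. Listing a physician's decision as consent withdrawal also obscures the reason in the patient-flow account.

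**Working it through.** The plan states no figure on this point, so there is none to reproduce. The check is a reading of the sections side by side, a count from the schedule, and an illustration on assumed rates.

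**1. What a postoperative 3b exit can remove.** Section 6 gives one intraoperative exposure per arm; for 5-FU this is 0.3 ml × 25 mg/ml = 7.5 mg. No later study dosing is described, so the exit removes none. The remaining study activity is the section 8 schedule.

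**2. What it ends.** Visits are at 1 day and at 1, 2, 4, 8, 12 and >24 weeks (7). Endoscopy is at 8, 12 and >24 weeks (3).

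| Exit after visit at | Visits lost | Endoscopies lost |
|---|---|---|
| 1 week | 5 of 7 | 3 of 3 |
| 2 weeks | 4 of 7 | 3 of 3 |
| 4 weeks | 3 of 7 | 3 of 3 |
| 8 weeks | 2 of 7 | 2 of 3 |
| 12 weeks | 1 of 7 | 1 of 3 |

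Any exit before the 8-week visit leaves the patient with no scheduled endoscopy.

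**3. How the safety comparison could be affected (assumed rates only).** Let e be the proportion with an early adverse event, f the share of those who exit, p1 the late-complication risk after an early event, and p0 the risk otherwise. Take p0, p1 and f as equal in both arms.

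- True late rate = (1 − e)·p0 + e·p1.
- Late rate among those still followed = [(1 − e)·p0 + e(1 − f)·p1] / [(1 − e) + e(1 − f)].

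Take f = 0.5.

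*Larger setting:* e = 5% control, 20% group B; p1 = 50%, p0 = 5%.
- True: 0.95×0.05 + 0.05×0.50 = 7.25%; 0.80×0.05 + 0.20×0.50 = 14.0%. Difference 6.75 points.
- Observed: 0.060/0.975 = 6.15%; 0.090/0.900 = 10.0%. Difference 3.85 points.

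*Smaller setting:* e = 5%, 10%; p1 = 30%, p0 = 10%.
- True: 0.95×0.10 + 0.05×0.30 = 11.0%; 0.90×0.10 + 0.10×0.30 = 12.0%. Difference 1.0 point.
- Observed: 0.1025/0.975 = 10.51%; 0.105/0.950 = 11.05%. Difference 0.54 points.

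The late difference shrinks in both settings. The amount depends entirely on the assumed values.

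**4. What is not lost.** The event that triggers the exit has already happened and been recognised, and nothing in section 10 removes it. In the larger setting, with 40 per arm, the comparison would still show 0.05×40 = 2 against 0.20×40 = 8 early events.

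**The case against.** The strongest reply is that the plan is silent, not wrong. It does not say that contact stops at exit, and physicians may well go on seeing these patients. Criterion 3b needs a physician's judgement, so it is not triggered by every adverse event. Leaving the study can also spare an injured patient study specimens and endoscopies. Single application is read without Sup.1.

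Much of this stands and limits the claim. That observation stops is an inference from the word exit. But the exit is a stated rule, no other section offsets it, and clinical contact outside the study supplies no data to section 10. Unsuitable procedures can be omitted without ending all observation.

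Four stronger readings are tempting, and the documents do not support them:
- *That exit criterion 1 is a second adverse-event exit after treatment.* It concerns patients who were not operated on, or whose operation could not sensibly continue.
- *That section 4 contradicts section 9.* Treating listed problems and keeping a discretionary exit are compatible, and section 9 does not mention exit.
- *That a harmful arm would look as safe as control.* Early events remain countable, as step 4 shows.
- *That the observed late difference would vanish.* This needs f = 1 and equal late risk in everyone else; criterion 3b does not send every patient with an early event out of the study.

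**Conclusion.** The concern holds in a limited form. As written, a postoperative 3b exit removes no described exposure to study material and ends the scheduled follow-up of patients with events judged serious. The index event is kept. Its outcome and any later complications are lost, selectively and possibly unequally by arm.

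What can be stated exactly is the loss per patient: 4 of 7 visits and 3 of 3 endoscopies for an exit after week 2. The effect on the group comparison cannot be sized, because the plan gives neither adverse-event nor exit rates; the figures in step 3 show direction only. The conclusion assumes that exit ends study observation and that Sup.1 adds no later application.

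**What to change.** - In section 4, state that for patients already operated on, a 3b event does not by itself end scheduled observation. They stay on the section 8 visits to 6 months unless they withdraw consent. Any study specimen or endoscopy may be omitted where the physician judges it unsuitable.
- Record the outcome of the event.
- Take item b out from under the consent heading. Record physician-decided exits and consent withdrawals as separate categories.
- In section 10, name all treated patients as the denominator for the complication and AE/SAE comparisons.

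Clinical care of the event is unchanged. The cost is an amended exit criterion and a sentence in section 10. The visits are already scheduled, so the added burden is the effort of retaining these patients. Follow-up that was never done cannot be recovered at analysis.
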